Intralevator trigger point injections with onabotulinumtoxinA has also been shown to improve pain in patients with chronic pelvic pain and is often the next step following steroid trigger point injections. Typically we use this for patients that respond to steroid TPIs but the effects are not long lasting. OnabotulinumtoxinA has been shown to provide relief for 6-9 months with minimal side effects including, infection, hematoma, and pain all of which are similar to traditional TPI¹⁶.

In a study of 30 patients that received 80 units of onabotulinumtoxinA and 30 patients that received placebo (saline) injection into the pelvic floor muscles for dysmenorrhea, dyspareunia, dyschezia, and nonmenstrual pelvic, there was a significant change in baseline in the onabotulinumtoxinA group in nonmenstrual pelvic pain¹⁸. Both groups had changes in dyspareunia and pelvic floor pressures (cm H20) but these patients were also allowed to undergo pelvic floor physical therapy during the course of treatment, which may have affected the results in both groups. OnabotulinumtoxinA 150U-400U has also been shown to be very effective in treatment of women with refractory vaginismus¹⁹.

OnabotulinumtoxinA injection has been compared to 80 mg methylprednisone injection in patients with chronic myofascial pain in the piriformis (100u), iliopsoas (150u) or scalenus anterior (80u) muscles and was found to have similar results at 30 days but at 60 days the onabotulinumtoxinA group had statistically significant improvements in their pain scores, compared to the methylprednisone group and also compared to their scores at 30 days²⁰.

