Subjects may be permitted to withdraw from the study if they have poor resolution of their pain or worsening of their symptoms. If they feel that they need other therapy during the first 30 days that is not permitted by the study (additional physical therapy, higher or more frequent doses of vaginal valium or pain medications, repeat TPI, etc.) they may be withdrawn and will be evaluated by the clinician for other treatment options. Patients who withdraw from the study will be asked if they are willing to fill out post questionnaires. Either group can get additional therapy following the first 30 days following the TPI. Furthermore, either group may have repeat TPI with kenalog one month following the original injection but patients may not undergo TPI with onabotulinumtoxinA following the original injection unless they withdraw from the study and are unblinded to prevent overdose of onabotulinumtoxinA. If additional TPIs with kenalog and ropivicaine are indicated at any of the follow up visits, the injections will be prepared and administered in the Woman's Urology Center, per routine standard of care. In no way will their withdrawal from the study impact what treatments will be offered to them. Subjects may also withdraw from the study without any reason given. If they do not feel comfortable continuing treatment by the study clinicians or at the WUC, they will be referred to another provider/site not involved in the study.

Schedule of Activities

| | Initial Visit | Treatment Visit | 30 days | 90 days | 180 days |
|--|----------------------|--|----------------------------|----------------------------|----------------------------|
| | Screening Consent | Baseline Questionnaires and physical exam (May be done at initial visit) | | | |
| Screening | x | | | | |
| Consent | X | | | | |
| Intake medical history form | X | X (If not done at initial visit) | | | |
| Urine pregnancy test ^a | x | | | | |
| Q tip test | X | X | Xp | Xp | Xp |
| Vaginal pH and wet mount | X | X (As needed) | X ^b (As needed) | X ^b (As needed) | X ^b (As needed) |
| Assess concomitant meds | X | X | Х | X | X |
| Vaginal exam assessment for high tone pelvic floor dysfunction with record of patient reported levator pain scores | X | X | Xp | Xp | Xb |
| Vital signs | X | X | Xb | Xb | Xp |
| Total overall pelvic pain score on VAS | x | X (done pre and post TPI) | X | x | X |
| BPI | | X | x | X | X |
| Trigger point injection | | X | As needed | As needed | As needed |

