A DOUBLE-BLIND, RANDOMIZED STUDY TO COMPARE ONOBOTULIUMTOXIN A VERSUS KENALOG FOR INTRAVAGINAL TRIGGER POINT INJECTIONS IN THE TREATMENT OF CHRONIC PELVIC PAIN

NCT: 02369068

STATISTICAL ANALYSIS PLAN

December 4, 2018

A DOUBLE-BLIND, RANDOMIZED STUDY TO COMPARE ONOBOTULIUMTOXIN A VERSUS KENALOG FOR INTRAVAGINAL TRIGGER POINT INJECTIONS IN THE TREATMENT OF CHRONIC PELVIC PAIN

Principal Investigator: [name], DO

Statistical Analysis Plan

This study is an exploratory pilot study. Descriptive statistics, provided for all variables, are the main focus of the analysis because of the small sample size. Descriptive statistics are reported with count (percentages) for categorical variables, and with mean (standard deviation) or median (range) for continuous variables, as appropriate.

Exploratory data analysis is focused on comparisons between the two treatment groups. Group differences for baseline variables and clinical characteristics at the time of treatment were performed. For each subject, the difference in their scores from baseline to one month, three months and six months were calculated, respectively.

Kruskal-Wallis tests were used to compare the medians between the groups for the Visual Analog Score (VAS) pain score, pain interference and pain severity. Fisher Exact tests were used for comparisons of distribution by group of pain assessment with the GRA questionnaire. The significance level was set at 0.05 without adjustment for the testing of the primary outcomes. No tests were performed at 3 and 6 months since 23.8% of the sample was missing due to drop out.

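### Further toxin requires study withdrawal and unblinding, and follow-up after withdrawal is voluntary and undated, so the 3- and 6-month data can lose women whose relief failed or faded

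*Protocol*

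**What the plan says.** The rules are in the protocol's intervention section, in the withdrawal text just before the Schedule of Activities.

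- Repeat steroid injection: "either group may have repeat TPI with kenalog one month following the original injection". No exit or unblinding is attached.
- Other therapy: "Either group can get additional therapy following the first 30 days following the TPI". Again no exit.
- Further toxin: not allowed after the study injection "unless they withdraw from the study and are unblinded to prevent overdose of onabotulinumtoxinA".
- Lack of effect: "Subjects may be permitted to withdraw from the study if they have poor resolution of their pain or worsening of their symptoms".
- Data after withdrawal: "Patients who withdraw from the study will be asked if they are willing to fill out post questionnaires". Instruments, dates and blinding status are not given.

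The Objectives section makes VAS, BPI and GRA at 3 and 6 months the secondary objective, hypothesises a longer-lasting effect of toxin, and asks what other treatments were needed (Appendix 4). It also places patients who need extra treatment in an intention-to-treat cohort, without a method. The SAP calculates changes from baseline to one, three and six months and then states: "No tests were performed at 3 and 6 months since 23.8% of the sample was missing due to drop out". It does not split drop-out by arm, visit or reason. It gives no missing-data method and no rule for scores taken after unblinding or re-treatment.

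**The concern.** Preventing overdose is a reason to break the code before more toxin is given. It is not a reason to stop collecting questionnaires, yet the protocol joins the two. Whether a woman stays under scheduled follow-up then depends on how her pain went and on which further treatment she has.

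Three results are exposed:

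- **The 3- and 6-month pain summaries.** They describe whoever stayed, and the hypothesis of longer effect rests on them.
- **The count of other treatments.** Appendix 4 is completed at 90 and 180 days. A woman who has repeat Kenalog is there to report it; a woman who left for toxin need not be.
- **Blinding of late scores.** VAS, BPI and GRA are all patient-reported. A withdrawn woman who does return a questionnaire may do so knowing her arm, and after a further toxin injection.

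**Working it through.** **1. Routes set side by side (protocol, intervention section)**

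| After the study injection | Stays in study? | Arm known? | 90/180-day questionnaires |
|---|---|---|---|
| Repeat Kenalog from one month | Yes | No requirement | Scheduled |
| Other therapy after 30 days | Yes | No requirement | Scheduled |
| Further toxin | No | Yes | Voluntary, undated |
| Withdrawal for poor relief | No | Not stated | Voluntary, undated |

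The last two rows are tied to relief that failed or did not last. The rules are the same in both arms.

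**2. The plan's only relevant figure**

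The SAP gives 23.8% without numerator or denominator. Among all fractions with a denominator from 20 to 63, only 5/21, 10/42 and 15/63 round to 23.8%. The protocol plans 40 to complete and up to 60 enrolled. Only 10/42 lies in that range, so it is plausible but cannot be confirmed. No share of it can be assigned to the toxin rule.

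**3. Illustration of what selective loss could do**

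Assumptions, none from the documents except the 1:1 allocation: 42 patients, 21 per arm; 10 drop-outs; response means counted as improved; every drop-out is a non-responder who returns nothing. This is the extreme case.

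Formula: observed response = (21 × true response) / (21 − drop-outs in the arm).

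Example, true response 50%, so 10.5 expected responders per arm: with 7 Kenalog and 3 toxin drop-outs, 10.5/14 = 75.0% and 10.5/18 = 58.3%.

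| Drop-outs Kenalog/toxin | True 50% vs 50%: Kenalog, toxin, toxin minus Kenalog | True 40% vs 60% (+20): Kenalog, toxin, toxin minus Kenalog |
|---|---|---|
| 5/5 | 65.6%, 65.6%, 0 | 52.5%, 78.8%, +26.3 |
| 7/3 | 75.0%, 58.3%, −16.7 | 60.0%, 70.0%, +10.0 |
| 8/2 | 80.8%, 55.3%, −25.5 | 64.6%, 66.3%, +1.7 |
| 10/0 | 95.5%, 50.0%, −45.5 | 76.4%, 60.0%, −16.4 |

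Equal loss of non-responders inflates both arms. Unequal loss can create, hide or reverse a difference. With equal true rates, swapping the split to 3/7 gives +16.7 instead of −16.7, so direction depends wholly on who left. At the other end, if drop-out is unrelated to outcome, expected observed response is 50% in each arm and there is no bias.

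**4. What a sensitivity summary does**

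Under the same assumptions, counting the withdrawals as not improved gives 10.5/21 = 50% in each arm, whatever the split. If some withdrawn women had in fact improved, it would understate response, so it is a bound to set beside the observed summary.

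**The case against.** Several stronger readings are tempting, and the documents do not support them.

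- **That toxin is the usual escalation after a failed first injection.** The Background does say toxin "is often the next step following steroid trigger point injections". Its next sentence says it is typically used for women who respond to steroid injections but whose relief does not last. The Background also describes three to five injections as typical. The usual next step after one injection may well be another of the same kind, which the protocol allows within the study. What stands is that toxin candidates include women whose relief faded, and they bear on duration of effect.
- **That this rule caused the 23.8% drop-out.** The SAP gives no reasons. Nobody is shown to have left for toxin, and withdrawn women are asked for questionnaires, so loss is possible, not certain.
- **That the results favour a particular arm.** The rule is identical in both arms. A spurious difference needs unequal exits, and the documents say nothing on that. Selective loss within an arm does not need it.
- **That the primary comparison is compromised.** The 30-day visit lists the questionnaires before new treatment is started, so a woman asking for toxin then would ordinarily have blinded scores already. The gap concerns exits between visits and later scores. Withdrawals within the first 30 days could touch the primary data, but extra therapy is restricted in that period.

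It is also fair that this is an exploratory, mainly descriptive pilot with no tests at 3 and 6 months, so no p-value is at stake. That limits the consequence. It does not help a reader of the late change scores, which the SAP still calculates.

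**Conclusion.** The point holds as a limit on the 3- and 6-month descriptive data and the other-treatments count. Under the protocol as written, women who seek toxin or withdraw for poor relief leave scheduled follow-up, while women who have other further treatment remain. The voluntary, undated request for questionnaires does not close that gap, and scores obtained that way may be unblinded.

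The size and direction of any bias are unknown. The illustrated differences, from 0 to 45.5 points in size when the true difference is zero, rest on an assumed 42 patients and on every drop-out being a non-responder with no later data. They show what is possible at this level of drop-out and are not an estimate for this trial.

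**What to change.** Leave the conditions for further treatment and for unblinding as they are. Change only what happens to data collection.

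1. State in the protocol that withdrawal from study treatment or from blinding is not withdrawal from follow-up.
2. For every woman who withdraws for toxin or for poor pain relief and does not refuse contact, collect VAS, BPI and GRA before the code is broken.
3. Then collect the scheduled 90- and 180-day questionnaires, including Appendix 4, by the mail and phone route the protocol already describes for follow-up visits not held in person.
4. In the SAP, report withdrawals by arm, reason, date and blinding status, and count further toxin by arm.
5. Show scores taken after unblinding or further toxin separately from the rest.
6. Add a sensitivity summary that counts withdrawal for lack of effect or for toxin as not improved.

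The SAP is written in the past tense with drop-out already known. For patients past follow-up, items 1 to 3 come too late. Items 4 to 6 still apply, as far as the reasons, dates and scores were recorded.

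The cost is protocol and consent wording, a few mailed questionnaires and a short table. Some late scores will be unblinded, and some women may decline.

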A DOUBLE-BLIND, RANDOMIZED STUDY TO COMPARE ONOBOTULIUMTOXIN A VERSUS KENALOG FOR INTRAVAGINAL TRIGGER POINT INJECTIONS IN THE TREATMENT OF CHRONIC PELVIC PAIN

NCT: 02369068

STATISTICAL ANALYSIS PLAN

December 4, 2018

A DOUBLE-BLIND, RANDOMIZED STUDY TO COMPARE ONOBOTULIUMTOXIN A VERSUS KENALOG FOR INTRAVAGINAL TRIGGER POINT INJECTIONS IN THE TREATMENT OF CHRONIC PELVIC PAIN

Principal Investigator: [name], DO

Statistical Analysis Plan

This study is an exploratory pilot study. Descriptive statistics, provided for all variables, are the main focus of the analysis because of the small sample size. Descriptive statistics are reported with count (percentages) for categorical variables, and with mean (standard deviation) or median (range) for continuous variables, as appropriate.

Exploratory data analysis is focused on comparisons between the two treatment groups. Group differences for baseline variables and clinical characteristics at the time of treatment were performed. For each subject, the difference in their scores from baseline to one month, three months and six months were calculated, respectively.

Kruskal-Wallis tests were used to compare the medians between the groups for the Visual Analog Score (VAS) pain score, pain interference and pain severity. Fisher Exact tests were used for comparisons of distribution by group of pain assessment with the GRA questionnaire. The significance level was set at 0.05 without adjustment for the testing of the primary outcomes. No tests were performed at 3 and 6 months since 23.8% of the sample was missing due to drop out.
